## 1.0 Surveillance Background

The goal of diabetes mellitus treatment is to maintain patients' QOLs as those in healthy people and to secure their lifetimes through management for a favorable blood glucose level for a long time. In particular, early drug treatment is considered important for patients with mild type 2 diabetes mellitus, which maintains a favorable blood glucose level and inhibits the diabetes progress, along with prevention of microangiopathy.

As an oral drug started to be administered early to patients with mild type 2 diabetes mellitus, the desirable drug should have a low risk of hypoglycemia, be well tolerable, and not exhaust pancreatic function.

DPP-4 inhibitors selectively inhibit DPP-4, increase blood GLP-1 levels, and prompt the pancreas to secrete insulin in a glucose level-dependent manner. Taken together, DPP-4 inhibitors are expected to be highly effective for patients with mild type 2 diabetes mellitus. As a DPP-4 inhibitor, Nesina tablets (generic name: alogliptin benzoate) are confirmed to be highly effective and safe when administered alone and combined with various oral diabetic drugs in clinical studies conducted in Japan. The following are approved indications for Nesina:

### Indications for Nesina tablets

#### Type 2 diabetes mellitus

However, this indication is limited only for patients who had an insufficient response to the following therapies:

- (1) Only diet and exercise therapies.
- (2)  $\alpha$ -glucosidase inhibitors used in addition to diet and exercise therapies.
- (3) Thiazolidines used in addition to diet and exercise therapies.
- (4) Sulfonylureas used in addition to diet and exercise therapies.
- (5) Biguanides used in addition to diet and exercise therapies.

However, the efficacy and safety of Nesina has not been well evaluated for patients with mild type 2 diabetes mellitus because Nesina tablets have been administered to type 2 diabetes mellitus patients with HbA1c of  $\geq 6.5\%$  (for patients treated with sulfonylureas, HbA1c of  $\geq 7.0\%$ ) in clinical studies conducted before drug approval.

Therefore, this Special Drug Use Surveillance (hereinafter, the Surveillance) was planned to evaluate the long-term safety and efficacy of Nesina tablets (hereinafter, Nesina) for patients with mild type 2 diabetes mellitus patients in a daily clinical practice.

## 2.0 Objectives of Surveillance

To examine the safety and efficacy of long-term treatment with alogliptin (Nesina) in patients with mild type 2 diabetes mellitus in the routine clinical setting.

### 3.0 Number of Planned Patients for Surveillance and the Rationales

#### 3.1 Number of Planned Patients for Surveillance

20000 patients

#### 3.2 Rationales

According to database of 16 hospitals in Japan, supplied by PPD of 142358 patients documented as visited from October to December 2010, 15141 were patients with type 2 diabetes mellitus. Of these, 4165 patients had HbA1c (JDS) of  $\leq 7.0\%$ , which were the target population in this Surveillance. For patients with indications for Nesina, in addition, 1864 patients (70.4%) received only diet and exercise therapies (no diabetic drugs); 226 patients (8.5%) received  $\alpha$ -glucosidase inhibitors; 175 patients (6.6%) received thiazolidines; 273 patients (10.3%) received sulfonylureas; 109 patients (4.1%) received biguanides (each drug was administered alone).

In order to identify adverse drug reactions with a frequency of  $\geq 0.5\%$  using  $\geq a 95\%$  confidence level, 600 patients will be required. Assuming that the proportion of drugs in patients with mild type 2 diabetes mellitus is same as the above, if data in 20000 patients with mild type 2 diabetes mellitus are collected in this Surveillance, 14084 patients will be required for Nesina treatment alone; 1708 patients will be required for combination with  $\alpha$ -glucosidase inhibitors; 1322 patients will be required for combination with thiazolidines; 2063 patients will be required for combination with sulfonylureas; 824 patients will be required for combination with biguanides. Since any combination can identify the adverse drug reactions with a frequency of  $\geq 0.5\%$  using  $\geq a 95\%$  confidence level, the number of planned patients for surveillance was established as 20000.

### 4.0 Patients for Surveillance

Patients with mild type 2 diabetes mellitus will be evaluated for this Surveillance. However, patients must meet the inclusion criteria and none of the exclusion criteria, described below. Refer to the Precaution with Respect to Indication in the package insert.

#### 4.1 Inclusion Criteria

Patients who meet the following criterion will be included in this Surveillance:

- (1) Patients with HbA1c (JDS value)  $\leq 7.0\%$  at the time of enrolment (within 3 months before initiation of Nesina therapy)  
\* Regardless of the use of antidiabetic medication

#### 4.2 Exclusion Criteria

Patients who meet any of the following criteria will be excluded from this Surveillance:

- (1) Patients with severe ketosis, diabetic coma or precoma, or type 1 diabetes mellitus
- (2) Patients with severe infection, pre- or post-operative patients, or patients with serious traumatic injury

(3) Patients with a history of hypersensitivity to any ingredient of Nesina

## 5.0 Dosage and Administration for Patients to be Surveyed

The usual adult dose of alogliptin is 25 mg administered orally once daily. Refer to the Precaution with Respect to Dosage and Administration in the package insert.

## 6.0 Number of To-be Survey Sites by Department

Internal medicine or other department: Approximately 1000 sites

## 7.0 Survey Methods

### 7.1 Observation Period

The observation period will be 36 months after the start date of Nesina treatment.

If Nesina treatment is discontinued for any reason, the survey will be ended at the discontinuation.

### 7.2 Request for Sites and Agreement

This surveillance will be conducted using the electronic data collection system via web **CCI** [REDACTED]. Before asking survey, MRs of Takeda Takeda Pharmaceutical Company Limited. (Hereinafter, Takeda MRs) will fully explain to the Investigator about the objectives, details, handling methods for **CCI** [REDACTED] and handling of electronic signature, user ID, and passwords, based on “Request for Cooperation of Special Drug Use Surveillance,” “Summary for Surveillance,” “Entry Screen Images,” and “Brief Manual for Handling of **CCI** [REDACTED] and will finalize written agreement with survey sites to ask requests for surveillance within the specified period.

### 7.3 Methods for Registration of Patients to be Surveyed

This Surveillance will be conducted using Central Registration System with **CCI** [REDACTED] The Investigator will enter registration data on **CCI** [REDACTED] (refer to Section 9.1) for patients who start Nesina treatment after the start date of agreement with a survey site, before 14 days after the start date of Nesina treatment (define the start date of treatment as “0 day” and one day after the start date of treatment as “1 day”).

### 7.4 Entry on Survey Sheet (Electronic) and Electronic Signature

The Investigator will enter patient demographic data and details of treatment on **CCI** [REDACTED] at each data entry time point (at the start of Nesina treatment, 3 months, 6 months, 12 months, 18 months, 24 months, 30 months, and 36 months after the start of Nesina treatment or treatment discontinuation). In addition, the Investigator will sign electronically on the survey sheet in **CCI** [REDACTED] for “Patient Demographic Data and Details of Treatment by 12 Months of Treatment” after 12 months of treatment and for Patient Demographic Data and Details of Treatment by 36 Months of Treatment” after 36 months of treatment.

For patients who discontinue treatment with Nesina during the observation period for any reason, the Investigator will enter the patient demographic data and details of treatment on **CCI** [REDACTED] and will sign electronically in the survey sheet around within 1 month after the end of necessary observation. However, for patients who discontinue treatment with Nesina due to an adverse event, the Investigator will continue observation after treatment discontinuation, wherever possible, until the adverse event resolve or is resolving and will enter the observation results on **CCI** [REDACTED] as well as sign electronically in the survey sheet.

In case that additional survey is required after Takeda checked the details, Takeda will ask request for re-survey on **CCI** [REDACTED]. The Investigator will check the details of request for re-survey and enter the re-survey results on **CCI** [REDACTED] as well as sign electronically in the survey sheet.

## 7.5 Measures for Development of Adverse Events

In case of development of an adverse event, the Investigator will contact the Takeda MR. If the Takeda MR requests additional detailed information, the Investigator will provide it.

## 8.0 Scheduled Survey Period

Survey period: July 2011 to January 31, 2017

Patient registration period: July 2011 to July 31, 2013Note)

Due date for entry of “Patient Data and Details of Treatment by 12 Months of Treatment:”  
August 31, 2014

Due date for entry of “Patient Data and Details of Treatment by 36 Months of Treatment:”  
August 31, 2016

Note) Patients who will be treated with Nesina by July 31, 2013 can be registered.

In case that the registered patients reach the scheduled number of patients to be surveyed before July 31 2013, the registration will close earlier than scheduled.

## 9.0 Matters to be Surveyed

The Investigator will enter data of the parameters described below on **CCI** [REDACTED]. The schedule of this surveillance is shown in the Appendix.

### 9.1 Patient Registration Data

#### 1) Matters to be surveyed

Start date of Nesina treatment, Patient ID Number, patient initial, sex, birth date, HbA1c (JDS) within 3 months prior to Nesina treatment, inclusion criteria assessment, and exclusion criteria assessment

#### 2) Survey period

At patient registration

### 9.2 Survey sheet: patient demographic data

#### 1) Matters to be surveyed

Diagnosis period of type 2 diabetes mellitus, height, practice category (at the start of survey), presence or absence of pregnancy (females only), pregnancy week (if applicable), severity of renal impairment, rationale for assessment of the severity of renal impairment, concurrent disease, prior medical history, alcohol history, smoking history, and presence or absence of dietary intervention / exercise intervention

2) Survey period

At the start of Nesina treatment

### 9.3 Survey sheet: details of treatment

1) Matters to be surveyed

Details of Nesina treatment (daily dose and administration period), status of end of Nesina treatment, reason for Nesina discontinuation (if applicable), details of other diabetic drug treatment\* (drug name, daily dose, route of administration, and administration period), and status of concomitant medications (other than diabetic drugs) (drug name, route of administration, administration period, and objectives of administration)

\* Diabetic drugs which are discontinued within 3 months prior to Nesina treatment are included.

2) Survey period

Period from the start of Nesina treatment to 36 months after treatment (or treatment discontinuation)

### 9.4 Laboratory/Observation Parameters

1) Matters to be surveyed

HbA1c (JDS, international standard value, or NGSP), fasting glucose, fasting insulin, fasting triglyceride, total cholesterol, HDL-cholesterol, LDL-cholesterol, weight, and blood pressure

2) Survey period

At the start of Nesina treatment, 3 months, 6 months, 12 months, 18 months, 24 months, 30 months, and 36 months of treatment (or treatment discontinuation)

### 9.5 Adverse Event

1) Matters to be surveyed

Presence or absence of adverse events (refer to Table 1), term of adverse events, onset date, seriousness and the reason (refer to Table 2), procedures related to Nesina, outcome, causal relationship to Nesina (refer to Table 3), presence or absence of diabetic complication (diabetic retinopathy, diabetic neuropathy, or diabetic nephropathy), change over time in clinically important laboratory values related to adverse events

If the outcome is assessed as Not resolved or Unknown and if the causal relationship cannot be assessed, the patient will be followed up, wherever possible. The detailed information (clinical course, laboratory tests for diagnosis, etc.) will be collected as possible for

development of hypoglycemia, tumor, pancreatitis, edema, angioedema-related symptom, immune system disorder, skin disorder and subcutaneous tissue disorder, cardiovascular system event (symptomatic coronary artery disease, cerebrovascular disorder, arteriosclerosis obliterans, cardiovascular death, sudden death, etc.)

2) Survey period

Period from the start of Nesina treatment to 36 months after treatment (or treatment discontinuation)

**Table 1 Definition of adverse event**

An adverse event (AE) is defined as any unfavorable event that develops after a pharmaceutical product is administered and which does not necessarily have a causal relationship with treatment. An adverse event can therefore be any unfavorable and unintended sign (including an abnormal laboratory finding, for example), symptom, or disease temporally associated with the use of a medicinal product, whether or not considered related to the medicinal product.

The following events will be handled as adverse events:

- Symptoms in infants breastfed by a Nesina taking mother
- Symptoms in children who received the relevant drug
- Symptoms in patients who received the relevant drug at a higher dose than approved or who took by themselves

**Table 2 Criteria for severity assessment**

|   |  |
|---|--|
| 
An event which meet any of the following criteria will be assessed as “Serious:”
 
 
1. Results in death (death).
 
2. Is life-threatening (potential death threat).
 
3. Requires inpatient hospitalization or prolongation of existing hospitalization (admission / prolonged hospitalization).
 
4. Results in persistent or significant disability/incapacity (disability).
 
5. Is a congenital anomaly/birth defect (congenital anomaly).
 
6. Other significant medical conditions which do not meet the above criteria 1 to 5. Events listed in the “Takeda Medically Significant AE List are included in this section criteria. (e.g., bronchospasm and the like, requiring a short-term intensive care in an emergency room and the like)
 
   |  |
| 
Takeda Medically Significant AE List
 
 
• Acute respiratory failure / acute respiratory distress syndrome (ARDS)
 
• Torsade de pointes / ventricular fibrillation / ventricular tachycardia
 
• Malignant hypertension
 
• Convulsive seizure (including convulsion and epilepsy)
 
• Agranulocytosis
 
• Aplastic anemia
 
• Toxic epidermal necrolysis / oculomucocutaneous syndrome (Stevens-Johnson syndrome)
 
• Hepatic necrosis
 
• Acute hepatic failure
 
• Anaphylactic shock
 
• Acute renal failure
 
• Pulmonary hypertension
 
• Pulmonary fibrosis (including interstitial pneumonia)
 
• Malignant syndrome / malignant hyperthermia
 
• Spontaneous abortion / stillbirth and fetal death
 
• Spread of infection via drug or suspected spread
 
• Endotoxic shock or suspected endotoxic shock
 
 |  |

**Table 3 Criteria for causality assessment between adverse events and Nesina**

| Assessment                        | Assessment criterion   |
|-----------------------------------|--|
| Related
(Suspectedly related)  | 
Temporally evident correlation (including the post-treatment clinical course) present.
 
Or an adverse event that may have been caused by the primary disease, concurrent disease, concomitant medication, or other factor including concomitant procedures, but also suggested to be caused by the relevant drug.
 |
| Not related
(Unlikely related) | No temporally evident correlation with the relevant drug. Or an adverse event presumably caused by the primary disease, concurrent disease, concomitant medication, or other factor.   |
| Not assessable                    | Lack of information for assessment of temporal correlation (including the post-treatment clinical course), the primary disease, concurrent   |

|  |   |
|--|---|
|  | disease, concomitant medication, other factor, etc. |
|--|---|

## 10.0 Analysis Parameters and Methods

### 10.1 Patient Component Parameters

The following will be tabulated: number of registered patients, number of survey sheet (electronic) collected patients, number of survey completer, number of survey discontinuations and the reason for discontinuation, number of the Safety Analysis Set, number of the Efficacy Analysis Set, and number of patients excluded from analysis and the reason for exclusion, etc.

### 10.2 Patient Demographics

The following patient demographics will be tabulated: age, sex, disease period, severity of renal impairment (including severity) (yes or no), concurrent disease, past medical history, alcohol history, smoking history, etc.

### 10.3 Details of Treatment

The following will be tabulated: status of Nesina treatment, status of concomitant medications (including the status of diabetic drugs at the start of Nesina treatment), etc.

### 10.4 Safety Parameters

The items described below will be tabulated in the Safety Analysis Set. Adverse events will be coded using the MedDRA and summarized by Preferred Term (PT) and System Organ Class (SOC).

#### 10.4.1 Occurrence of Adverse Drug Reactions

The type, seriousness, onset period, and the like for adverse drug reactions reported in the observation period will be tabulated.

#### 10.4.2 Factors Probably Affecting Safety

For adverse drug reactions reported in the observation period, the frequency of patient demographics (e.g., age, sex), details of treatment (e.g., status of Nesina, and status of concomitant medications) will be stratified.

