**Table 3 Criteria for causality assessment between adverse events and Nesina**

| Assessment                        | Assessment criterion  |
|-----------------------------------|---|
| Related
(Suspectedly related)  | Temporally evident correlation (including the post-treatment clinical course) present.
Or an adverse event that may have been caused by the primary disease, concurrent disease, concomitant medication, or other factor including concomitant procedures, but also suggested to be caused by the relevant drug. |
| Not related
(Unlikely related) | No temporally evident correlation with the relevant drug. Or an adverse event presumably caused by the primary disease, concurrent disease, concomitant medication, or other factor.  |
| Not assessable                    | Lack of information for assessment of temporal correlation (including the post-treatment clinical course), the primary disease, concurrent disease, concomitant medication, other factor, etc.  |

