5.4 Patient Demographics and Frequency of Adverse Drug Reactions / Infections by Treatment

5.4.1 Patients demographics and Frequency of Adverse Drug Reactions / Infections by Treatment

(1) Patients to be tabulated and analyzed

Safety Analysis Set

(2) Details of tabulation and analysis

Each parameter will be categorized by the categories described below to tabulate the percent of patients with adverse drug reactions, etc.

The Fischer exact test will be used for parameters without rank data. The Mann-Whitney U test will be used for parameters with rank data. (The tests will be used for parameters with asterisk [*].)

Total and mild type 2 diabetes mellitus patients will be tabulated.

Parameter	Category
Sex*	Male, Female
Age*	< 65 years, ≥65 years
	< 75 years, ≥75 years
Severity of renal impairment*	Normal + Mild, Moderate + Severe
Concurrent liver disorder*	No, Yes
Concurrent renal disorder*	No, Yes
Concurrent heart disease*	No, Yes
Details of concurrent heart disease	Cardiac failure, myocardial infarction, or angina pectoris

Parameter	Category
(overlapped)	
Concurrent cardiac failure*	No, Yes
Severity classification of cardiac failure (NYHA classification)*	Classes NYHA I, NYHA II, NYHA III, and NYHA IV
Concurrent stroke-related disease*	No, Yes
Mean daily dose of Nesina	> 25 mg, 25 to >12.5 mg, 12.5 to > 6.25 mg, or ≤6.25 mg
Administration of concomitant medication (diabetic drug)	No, Yes
Concomitant medications (diabetic drugs) (overlapped)	α-glucosidase inhibitors, thiazolidines, sulfonylureas, biguanides, rapid-acting insulin secretagogues, or insulin preparations
Administration of concomitant medication (protease drug)*	No, Yes
Administration of concomitant medication (combined with renal excretory drug)*	No, Yes

(3) Number of tables and figures

Table 5.4.1-1

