5.17 Occurrence of Adverse Drug Reactions / Infections by Concomitant Medication (Diabetic Drug)

(1) Patients to be tabulated and analyzed

Safety Analysis Set

(2) Details of tabulation and analysis

Concomitant medications (diabetic drugs) will be classified into the following drugs: α -glucosidase inhibitors, thiazolidines, sulfonylureas, biguanides, rapid-acting insulin secretagogues, or insulin preparations, for tabulation of type of adverse drug reactions, etc.

The method for tabulation of adverse drug reactions, etc. is same as that described in Section 5.1.

Total and mild type 2 diabetes mellitus patients will be tabulated.

(3) Number of tables and figures

Table 5.17-1

5.18 Occurrence of Adverse Drug Reactions / Infections by Presence of Concomitant Protease Inhibitors

- (1) Patients to be tabulated and analyzed

Safety Analysis Set

- (2) Details of tabulation and analysis

Concomitant protease inhibitor will be classified into yes or no for tabulation of type of adverse drug reactions, etc.

The method for tabulation of adverse drug reactions, etc. is same as that described in Section 5.1.

Total and mild type 2 diabetes mellitus patients will be tabulated.

- (3) Number of tables and figures

Table 5.18-1

5.19 Occurrence of Adverse Drug Reactions / Infections by Presence of Concomitant Renal Excretory

Drug

- (1) Patients to be tabulated and analyzed

Safety Analysis Set

- (2) Details of tabulation and analysis

Concomitant renal excretory drug be classified into yes or no for tabulation of type of adverse drug reactions, etc.

The method for tabulation of adverse drug reactions, etc. is same as that described in Section 5.1.

Total and mild type 2 diabetes mellitus patients will be tabulated.

- (3) Number of tables and figures

Table 5.19-1

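### The ADR-only factor tests use factors that the causality rule also treats as alternative causes, and no all-cause table by factor shows whether grading has shifted the comparison

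*Protocol*

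**What the plan says.** **Grading rule (Protocol 9.5, Table 3; same text in every protocol version in the file).** One route to Not related is: "Or an adverse event presumably caused by the primary disease, concurrent disease, concomitant medication, or other factor". The Related row covers events that may have such another cause, "but also suggested to be caused by the relevant drug".

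**Factor analysis.** Protocol 10.4.2 stratifies ADRs by factor and names no test: "For adverse drug reactions reported in the observation period, the frequency of patient demographics (e.g., age, sex), details of treatment". The tests are in SAP 5.4.1: "Each parameter will be categorized by the categories described below to tabulate the percent of patients with adverse drug reactions, etc". On method: "The Fischer exact test will be used for parameters without rank data. The Mann-Whitney U test will be used for parameters with rank data". On scope: "The tests will be used for parameters with asterisk". The level is two-sided 5% (SAP 1.4), and no adjustment is named.

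The starred rows that matter here are:
- seven disease or renal rows: severity of renal impairment, "Concurrent liver disorder", and concurrent renal disorder, heart disease, cardiac failure, NYHA class and stroke-related disease;
- two drug rows: protease drug and renal excretory drug.

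Sex and age are also starred, but Table 3 does not name them. Concomitant diabetic drugs have no star. SAP 5.7 to 5.13 and 5.16 to 5.19 tabulate types of ADR by the same factors, including 5.17, "Occurrence of Adverse Drug Reactions / Infections by Concomitant Medication (Diabetic Drug".

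**All-cause events.** SAP 5.1.1, 5.1.3 and 5.2.1 tabulate them for total and mild patients only. None is split by a 5.4.1 factor.

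**ADR definition.** SAP 1.1 (all three versions) literally defines ADRs as events the investigator assessed as Not related.

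**The concern.** For nine starred rows, the factor under test is of a kind that the investigator may cite when deciding whether an event counts as an ADR at all. If a drug-caused event in a patient with heart disease is put down to the heart disease more readily than the same event would be explained away in a patient without it, the ADR rate in the heart-disease group falls for a reason unrelated to risk. A real excess could be hidden, or an apparently lower risk could reach significance, in patients where extra harm is a natural worry.

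The descriptive diabetic-drug tables (5.16, 5.17) have the same weakness. Hypoglycaemia attributed wholly to a sulfonylurea leaves the ADR table, and no table shows all-cause hypoglycaemia by sulfonylurea use. With no all-cause breakdown, a difference in grading cannot be told from a difference in risk.

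**Working it through.** **1. The plan's own figure.** Protocol 3.2 gives 600 patients to detect an ADR of frequency 0.5% with 95% confidence. ln(0.05)/ln(0.995) rounds up to 598; the rule of three gives 3/0.005 = 600; 1 − 0.995^600 = 0.9506. The figure reproduces and is not in dispute. It concerns seeing at least one case, not comparing groups.

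**2. Simple regrading.** From the documents: 20000 patients (Protocol 3.1), Fisher's exact test (SAP 5.4.1), two-sided 5% (SAP 1.4). Assumed, because the documents give none: how common the factor is, the true ADR risk p (equal in both groups), and the fraction g of factor-group ADRs regraded as Not related. Nothing is misgraded in the other group. The observed factor-group risk is p(1 − g). Simulated with 2000 runs per case:

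| With v without factor | p | g | Observed risks | P(false significantly lower risk) |
|---|---|---|---|---|
| 3000 v 17000 | 5% | 10% | 4.5% v 5.0% | about 0.2 |
| 3000 v 17000 | 5% | 20% | 4.0% v 5.0% | about 0.67 |
| 3000 v 17000 | 5% | 30% | 3.5% v 5.0% | about 0.96 |
| 2000 v 18000 | 3% | 20% | 2.4% v 3.0% | about 0.3 |
| 3000 v 17000 | 1% | 20% | 0.8% v 1.0% | about 0.15 |
| 600 v 19400 | 5% | 20% | 4.0% v 5.0% | about 0.17 |
| 600 v 19400 | 3% | 20% | 2.4% v 3.0% | about 0.10 |

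Without regrading this probability is about 0.025. For masking, take a true risk ratio of 1.5 on a base of 3% (3000 v 17000): power is about 0.98 with no regrading, about 0.4 at 20% (observed 3.6% v 3.0%) and about 0.02 at one third (3.0% v 3.0%).

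**3. Both kinds of grading error.** Let d be the drug-caused risk, b the background risk, s the chance that a drug-caused event is graded Related, and f the same chance for a background event. Observed ADR risk = d·s + b·f. Assume d = 3% in both groups (true ratio 1.00), and b = 10% without and 20% with the factor.

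- s falls from 0.9 to 0.6 with the factor, f = 0: 1.80%/2.70% = **0.67**.
- Same s, f falls from 0.10 to 0.05: 2.80%/3.70% = **0.76**.
- s falls from 0.9 to 0.75, f = 0.10 in both: 4.25%/3.70% = **1.15**.
- s falls from 0.9 to 0.6, f = 0.20 in both: 5.80%/4.70% = **1.23**.
- Equal s and f = 0: the ratio is the true one, so no bias.

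Across these cases a true ratio of 1.00 shows as anything from 0.67 to 1.23.

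**4. All-cause events alone.** The ratio is (3% + 20%)/(3% + 10%) = 1.77 at a true drug-caused ratio of 1.00. The all-cause column errs upward, so it cannot replace the ADR column.

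**5. The literal SAP 1.1 definition.** If ADR means graded Not related, the first case of step 3 gives (3% × 0.4 + 20%)/(3% × 0.1 + 10%) = 21.2%/10.3% = 2.06. The direction reverses.

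**The case against.** A reader might infer that these tests are biased downward, full stop. The documents do not support that. Table 3 keeps an event as Related when the drug is also suspected, so having a concurrent disease does not by itself remove the event. Correctly excluding an event the drug did not cause is not bias. Patients without the factor can also have events graded Not related, since the same row lists the primary disease and other factors. Background events graded Related push upward, as step 3 shows. Bias needs drug-caused events to be misgraded more often when the factor is present, and the documents give no such rate. All of this stands, and it limits the point to possible bias, most plausibly downward.

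A reader might also infer that the sulfonylurea example can yield a false significant result. It cannot, because the diabetic-drug rows are not tested. Nor does the point reach age, sex or Nesina dose, which Table 3 does not list as alternative causes.

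The higher probabilities in step 2 depend on a common factor, a fairly frequent ADR and error-free grading elsewhere; the lower rows show how quickly they fall. Finally, this is a single-arm surveillance sized on ADR frequency, its tables are largely descriptive, and 5.1.3 does report all-cause hypoglycaemia and cardiovascular events overall. That lowers the stakes but does not supply the missing breakdown.

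**Conclusion.** The point holds as a conditional one. For the seven disease or renal rows and two drug rows tested in SAP 5.4.1, the outcome depends on a judgement that may cite the same kind of factor, and the plan has nothing that would reveal a grading effect. The comparisons may be biased, most plausibly towards lower risk, if drug-caused events are graded Not related more often in patients with the factor. The size is illustrative only: a false significantly lower risk with probability about 0.2 at 10% regrading and 0.67 at 20% (3000 v 17000, equal true risk 5%), and about 0.10 to 0.17 at 20% regrading for a factor present in 3% of patients or an ADR risk of 1%. SAP 5.16 and 5.17 share the weakness descriptively. The direction assumes that ADR means an event not graded Not related, which SAP 1.1 literally contradicts. This is a cheap improvement, not a fault that invalidates the analysis.

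**What to change.** 1. Correct the SAP 1.1 definitions of ADRs and serious ADRs first; until then, the direction of any factor comparison is undefined.
2. For the disease, renal and concomitant-drug rows of 5.4.1, and the matching tables 5.7 to 5.13 and 5.16 to 5.19, add a parallel column for all adverse events regardless of causality, and the share of events graded Not related at each factor level.
3. Tabulate all-cause hypoglycaemia by concomitant diabetic drug.
4. State that ADR differences for these factors will be read together with the all-cause column. Do not require the two to agree: the concurrent disease itself raises all-cause rates (1.77 at a true ratio of 1.00 in step 4), so agreement would discriminate little.

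The cost is a few extra columns and one table, from data already collected under Protocol 9.5. The downside is that all-cause rates include events of the concurrent disease, so neither column can be read alone.
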